9.4 Informed Consent

Before each patient undergoes any protocol required assessments or procedure, the written informed consent will be obtained according to the regulatory and legal requirements of the participating country. As part of this procedure, the principal Investigator must explain orally and in writing the nature, duration, and purpose of the study, and the action of the drug in such a manner that the study patient should be informed that he/she is free to withdraw from the study at any time. He/she will receive all information that is required by federal regulations and ICH guidelines. The principal Investigator or designee will provide the sponsor with a copy of the IRB-approved ICF prior to the start of the study.

The informed consent document must be signed and dated; 1 copy will be handed to the patient and the principal Investigator will retain a copy as part of the clinical study records. The principal Investigator will not undertake any investigation specifically required for the clinical study until written consent has been obtained. The terms of the consent and when it was obtained must also be documented.

If the informed consent document is revised, it must be reviewed and approved by the responsible IRB/IEC. Patients currently enrolled may need to sign this revision (based on IRB/IEC requirements) and all future patients enrolled in the clinical study will be required to sign this revised ICF.

9.5 Records Management

The principal Investigator will ensure the accuracy, completeness, and timeliness of the data reported to the sponsor. Data collection processes and procedures will be reviewed and validated to ensure completeness, accuracy, reliability, and consistency. A complete audit trail will be maintained of all data changes. The principal Investigator or designee will cooperate with the sponsor's representative(s) for the periodic review of study documents to ensure the accuracy and completeness of the data capture system at each scheduled monitoring visit.

Electronic consistency checks and manual review will be used to identify any errors or inconsistencies in the data. This information will be provided to the respective study sites by means of electronic or manual queries.

The principal Investigator or designee will prepare and maintain adequate and accurate study documents (medical records, ECGs, AE and concomitant medication reporting, raw data collection forms, etc.) designed to record all observations and other pertinent data for each patient receiving BOS161721 or placebo.

The principal Investigator will allow sponsor representatives, contract designees, authorized regulatory authority inspectors, and the IRB to have direct access to all documents pertaining to the study.

Electronic case report forms are required and should be completed for each randomized patient. It is the principal Investigator's responsibility to ensure the accuracy, completeness, legibility, and timeliness of the data reported on the patients' eCRF. Electronic case report forms should be completed in a timely fashion to support the study timelines. Source documentation supporting the eCRF data should indicate the patient's participation in the study and should document the dates and details of study procedures, AEs, and patient status. The principal Investigator or designated representative should complete and the principal Investigator should verify the source documents as the information is collected. Any outstanding entries must be completed immediately after the final examination. An explanation should be given for all missing data.

The principal Investigator will ensure the accuracy, completeness, and timeliness of the data reported to the Sponsor. Data collection processes and procedures will be reviewed and validated to ensure completeness, accuracy, reliability, and consistency. A complete audit trail will be maintained of all data changes.

9.6 Source Documentation

The documents that will form the source data for the clinical study (e.g., patient charts, laboratory reports) must be defined and documented in the in-house study master file prior to the start of the study. Data on the eCRFs which will be checked against source data during monitoring visits must also be defined and documented in the in-house study master file including the percentage of each of the source data to be verified and the percentage of patients' eCRFs to be monitored.

9.7 Study Files and Record Retention

According to ICH guidelines, essential documents should be retained for a minimum of 2 years after the last approval of a marketing application in an ICH region and until there are no pending or contemplated marketing applications in an ICH region or at least 2 years have elapsed since the formal discontinuation of clinical development of BOS161721. However, these documents should be retained for a longer period if required by the applicable legal requirements.

10 AUDITING AND MONITORING

Throughout the course of the study, the study monitor will make frequent contacts with the Investigator. This will include telephone calls and on-site visits. The study will be routinely monitored to ensure compliance with the study protocol and the overall quality of data collected. During the on-site visits, the eCRFs will be reviewed for completeness and adherence to the protocol. As part of the data audit, source documents will be made available for review by the study monitor. The study monitor may periodically request review of the Investigator study file to assure the completeness of documentation in all respects of clinical study conduct. The study monitor will verify that each patient has proper consent documentation from the patient and/or patient's authorized representative for study procedures and for the release of medical records to the sponsor, FDA, other regulatory authorities, and the IRB. The study monitor will also verify that assent was obtained for patients not capable of providing informed consent or that documentation is provided by the Investigator explaining why the patient was unable to provide assent. The Investigator or appointed delegate will receive the study monitor during these on-site visits and will cooperate in providing the documents for inspection and respond to inquiries. In addition, the Investigator will permit inspection of the study files by authorized representatives of the regulatory agencies. On completion of the study, the study monitor will arrange for a final review of the study files after which the files should be secured for the appropriate time period.

Throughout the course of the study, the medical monitor will determine eligibility of all screened patients, will address any medical issues that might arise, clarify medical questions, review patient safety data (e.g., AE/SAE, laboratory, and ECG), and partner with the study team in the overall study management. The study medical monitoring plan will document additional details of the study medical oversight and monitoring.

11 AMENDMENTS

Protocol modifications, except those intended to reduce immediate risk to study patients, may be made only by Boston Pharmaceuticals. A protocol change intended to eliminate an apparent immediate hazard to patients may be implemented immediately, provided the IRB/IEC is notified within 5 days.

Any permanent change to the protocol must be handled as a protocol amendment. The written amendment must be submitted to the IRB/IEC and the Investigator must await approval before implementing the changes. Boston Pharmaceuticals will submit protocol amendments to the appropriate regulatory authorities for approval.

If in the judgment of the IRB/IEC, the Investigator, and/or Boston Pharmaceuticals, the amendment to the protocol substantially changes the study design and/or increases the potential risk to the patient and/or has an impact on the patient's involvement as a study participant, the currently approved written ICF will require similar modification. In such cases, informed consent will be renewed for patients enrolled in the study before continued participation.

12 STUDY REPORT AND PUBLICATIONS

Boston Pharmaceuticals is responsible for preparing and providing the appropriate regulatory authorities with clinical study reports according to the applicable regulatory requirements.

By signing the protocol, the principal Investigator agrees with the use of results of the clinical study for the purposes of national and international registration, publication, and information for medical and pharmaceutical professionals. If necessary, the competent authorities will be notified of the principal Investigator's name, address, qualifications, and extent of involvement.

The principal Investigator shall not publish any data (poster, abstract, paper, etc.) without having consulted and obtained approval from the sponsor in advance.

13 STUDY DISCONTINUATION

Both Boston Pharmaceuticals and the principal Investigator reserve the right to terminate the study at the Investigator's site at any time. Should this be necessary, Boston Pharmaceuticals or a specified designee will inform the appropriate regulatory authorities of the termination of the study and the reasons for its termination, and the principal Investigator will inform the IRB/IEC of the same. In terminating the study Boston Pharmaceuticals and the principal Investigator will assure that adequate consideration is given to the protection of the patients' interests.

14 CONFIDENTIALITY

All information generated in this study is considered highly confidential and must not be disclosed to any person or entity not directly involved with the study unless prior written consent is gained from Boston Pharmaceuticals, except to the extent necessary to obtain informed consent from patients who wish to participate in the trial or to comply with regulatory requirements. However, authorized regulatory officials, IRB/IEC personnel, Boston Pharmaceuticals, and its authorized representatives are allowed full access to the records.

Identification of patients and eCRFs shall be by initials, birthdate, or patient number. Documents that identify the patient (e.g., the signed informed consent document) must be maintained in confidence by the principal Investigator. If required, the patient's full name may be made known to an authorized regulatory agency or other authorized official.

16.2 Appendix 2: Declaration of Helsinki

WORLD MEDICAL ASSOCIATION DECLARATION OF HELSINKI

Ethical Principles For Medical Research Involving Human Subjects.

Adopted by the 18th WMA General Assembly
Helsinki, Finland, June 1964
and amended by the
29th WMA General Assembly, Tokyo, Japan, October 1975
35th WMA General Assembly, Venice, Italy, October 1983
41st WMA General Assembly, Hong Kong, September 1989
48th WMA General Assembly, Somerset West, Republic of South Africa, October 1996
and the
52nd WMA General Assembly, Edinburgh, Scotland, October 2000

A. INTRODUCTION

The World Medical Association has developed the Declaration of Helsinki as a statement of ethical principles to provide guidance to physicians and other participants in medical research involving human subjects. Medical research involving human subjects includes research on identifiable human material or identifiable data.

It is the duty of the physician to promote and safeguard the health of the people. The physician's knowledge and conscience are dedicated to the fulfillment of this duty.

The Declaration of Geneva of the World Medical Association binds the physician with the words, "The health of my subject will be my first consideration," and the International Code of Medical Ethics declares that, "A physician shall act only in the subject's interest when providing medical care which might have the effect of weakening the physical and mental condition of the subject".

Medical progress is based on research, which ultimately must rest in part on experimentation involving human subjects.

In medical research on human subjects, considerations related to the well-being of the human subject should take precedence over the interests of science and society.

The primary purpose of medical research involving human subjects is to improve prophylactic, diagnostic, and therapeutic procedures and the understanding of the etiology and pathogenesis of disease. Even the best-proven prophylactic, diagnostic, and therapeutic methods must continuously be challenged through research for their effectiveness, efficiency, accessibility, and quality.

In current medical practice and in medical research, most prophylactic, diagnostic, and therapeutic procedures involve risks and burdens.

Medical research is subject to ethical standards that promote respect for all human beings and protect their health and rights. Some research populations are vulnerable and need special protection. The particular needs of the economically and medically disadvantaged must be recognized. Special attention is also required for those who cannot give or refuse consent for themselves, for those who may be subject to giving consent under duress, for those who will not benefit personally from the research and for those for whom the research is combined with care.

Research Investigators should be aware of the ethical, legal, and regulatory requirements for research on human subjects in their own countries as well as applicable international requirements. No national ethical, legal, or regulatory requirement should be allowed to reduce or eliminate any of the protections for human subjects set forth in this Declaration.

B. BASIC PRINCIPLES FOR ALL MEDICAL RESEARCH

It is the duty of the physician in medical research to protect the life, health, privacy, and dignity of the human subject.

Medical research involving human subjects must conform to generally accepted scientific principles, be based on a thorough knowledge of the scientific literature, other relevant sources of information, and on adequate laboratory and, where appropriate, animal experimentation.

Appropriate caution must be exercised in the conduct of research, which may affect the environment, and the welfare of animals used for research must be respected.

The design and performance of each experimental procedure involving human subjects should be clearly formulated in an experimental protocol. This protocol should be submitted for consideration, comment, guidance, and where appropriate, approval to a specially appointed ethical review committee, which must be independent of the Investigator, the sponsor or any other kind of undue influence. This independent committee should be in conformity with the laws and regulations of the country in which the research experiment is performed. The committee has the right to monitor ongoing trials. The researcher has the obligation to provide monitoring information to the committee, especially any SAEs. The researcher should also submit to the committee, for review, information regarding funding, sponsors, institutional affiliations, other potential conflicts of interest and incentives for subjects.

The research protocol should always contain a statement of the ethical considerations involved and should indicate that there is compliance with the principles enunciated in this Declaration.

Medical research involving human subjects should be conducted only by scientifically qualified persons and under the supervision of a clinically competent medical person. The responsibility for the human subject must always rest with a subject of the research, even though the subject has given consent.

Every medical research project involving human subjects should be preceded by careful assessment of predictable risks and burdens in comparison with foreseeable benefits to the subject or to others. This does not preclude the participation of healthy volunteers in medical research. The design of all studies should be publicly available.

Physicians should abstain from engaging in research projects involving human subjects unless they are confident that the risks involved have been adequately assessed and can be satisfactorily managed. Physicians should cease any investigation if the risks are found to outweigh the potential benefits or if there is conclusive proof of positive and beneficial results.

Medical research involving human subjects should only be conducted if the importance of the objective outweighs the inherent risks and burdens to the subject. This is especially important when the human subjects are healthy volunteers.

Medical research is only justified if there is a reasonable likelihood that the populations in which the research is carried out stand to benefit from the results of the research.

The subjects must be volunteers and informed participants in the research project.

The right of research subjects to safeguard their integrity must always be respected. Every precaution should be taken to respect the privacy of the subject, the confidentiality of the subject's information and to minimize the impact of the study on the subject's physical and mental integrity and on the personality of the subject.

In any research on human beings, each potential subject must be adequately informed of the aims, methods, sources of funding, any possible conflicts of interest, institutional affiliations of the researcher, the anticipated benefits and potential risks of the study and the discomfort it may entail. The subject should be informed of the right to abstain from participation in the study or to withdraw consent to participate at any time without reprisal. After ensuring that the subject has understood the information, the physician should then obtain the subject's freely-given informed consent, preferably in writing. If the consent cannot be obtained in writing, the non-written consent must be formally documented and witnessed.

When obtaining informed consent for the research project the physician should be particularly cautious if the subject is in a dependent relationship with the physician or may consent under duress. In that case the informed consent should be obtained by a well-informed physician who is not engaged in the investigation and who is completely independent of this relationship.

For a research subject who is legally incompetent, physically or mentally incapable of giving consent or is a legally incompetent minor, the Investigator must obtain informed consent from the legally authorized representative in accordance with applicable law. These groups should not be included in research unless the research is necessary to promote the health of the population represented and this research cannot instead be performed on legally competent persons.

When a subject deemed legally incompetent, such as a minor child, is able to give assent to decisions about participation in research, the Investigator must obtain that assent in addition to the consent of the legally authorized representative.

Research on individuals from whom it is not possible to obtain consent, including proxy or advance consent, should be done only if the physical/mental condition that prevents obtaining informed consent is a necessary characteristic of the research population. The specific reasons for involving research subjects with a condition that renders them unable to give informed consent should be stated in the experimental protocol for consideration and approval of the review committee. The protocol should state that consent to remain in the research should be obtained as soon as possible from the individual or a legally authorized surrogate.

Both authors and publishers have ethical obligations. In publication of the results of research, the Investigators are obliged to preserve the accuracy of the results. Negative as well as positive results should be published or otherwise publicly available. Sources of funding, institutional affiliations and any possible conflicts of interest should be declared in the publication. Reports of experimentation not in accordance with the principles laid down in this Declaration should not be accepted for publication.

C. ADDITIONAL PRINCIPLES FOR MEDICAL RESEARCH COMBINED WITH MEDICAL CARE

The physician may combine medical research with medical care, only to the extent that the research is justified by its potential prophylactic, diagnostic, or therapeutic value. When medical research is combined with medical care, additional standards apply to protect the subjects who are research subjects.

The benefits, risks, burdens, and effectiveness of a new method should be tested against those of the best current prophylactic, diagnostic, and therapeutic methods. This does not exclude the use of placebo, or no treatment, in studies where no proven prophylactic, diagnostic, or therapeutic method exists.

At the conclusion of the study, every subject entered into the study should be assured of access to the best-proven prophylactic, diagnostic, and therapeutic methods identified by the study.

The physician should fully inform the subject which aspects of the care are related to the research. The refusal of a subject to participate in a study must never interfere with the subject-physician relationship.

In the treatment of a subject, where proven prophylactic, diagnostic, and therapeutic methods do not exist or have been ineffective, the physician, with informed consent from the subject, must be free to use unproven or new prophylactic, diagnostic, and therapeutic measures, if in the physician's judgment it offers hope of saving life, re-establishing health, or alleviating suffering. Where possible, these measures should be made the object of research, designed to evaluate their safety and efficacy. In all cases,

new information should be recorded and, where appropriate, published. The other relevant guidelines of this Declaration should be followed.

16.3 Appendix 3: Commonly Used Corticosteroid Equivalents

Medication	Prednisone Dose Equivalence
Prednisone	1 mg
Cortisone	5 mg
Hydrocortisone	4 mg
Prednisolone	1 mg
Methylprednisolone	0.8 mg
Triamcinolone	0.8 mg
Budesonide	0.25 mg
Dexamethasone	0.16 mg
Bethamethasone	0.16 mg

16.4 Appendix 4: Medication Washout Periods

WASHOUT TIMES OF MEDICATIONS BASED ON 5 HALF-LIVES

Medication	Discontinuing Prior to Signing Consent
Abatacept (CTLA4Ig)	24 weeks
Alefacept	12 weeks
AMG 623 (blisibimod)	24 weeks
Anifrolumab	12 weeks
Atacept (TACI-Ig)	12 weeks
Belimumab	24 weeks
Cyclophosphamide	24 weeks
Cyclosporine (except for CSA eye drops)	4 weeks for oral and 8 weeks for topical
Danazol	4 weeks
Dapsone	4 weeks
Eculizumab	12 weeks
Efalizumab	12 weeks
Epratuzumab	24 weeks
Intravenous globulin	4 weeks
Leflunomide	8 weeks (4 weeks for washout with cholestyramine)
Lenalidomide with cholestyramine	8 weeks
Lupuzor	12 weeks
Memantine	4 weeks
Natalizumab	24 weeks
Ocrelizumab	48 weeks (or 24 weeks with recovery of B cell)
Pimecrolimus	4 weeks
Plasmapheresis	24 weeks
Retinoids (oral or topical)	4 weeks
Rituximab	48 weeks (or 24 weeks with recovery of B cell)
Sirolimus	4 weeks
Tacrolimus	4 weeks
Thalidomide	8 weeks
Tocilizumab	12 weeks

16.5 Appendix 5: BILAG-2004 (Study-Specific Modified Criteria)

CCI
[Redacted text block]

- [Redacted text block]

[Redacted text block]

[Redacted text block]

[Redacted text block]

16.6 Appendix 6: Injection Site Reaction Grading Scale

Adverse event Injection site reaction	Grade 1	Grade 2	Grade 3	Grade 4	Grade 5
Definition: A disorder characterized by an intense adverse reaction (usually immunologic) developing at the site of an injection	Tenderness with or without associated symptoms (e.g., warmth, erythema, itching)	Pain; Lipodystrophy; Edema; phlebitis	Ulceration or necrosis; Severe tissue damage; Operative intervention indicated	Life-threatening consequences; urgent intervention indicated	Death
Pain	Mild pain	Moderate pain; limiting instrumental ADL	Severe pain; limiting self-care ADL	-	-
Rash maculopapular/Erythema/Induration Definition: A disorder characterized by the presence of macules (flat) and papules (elevated). Also known as morbilliform rash, it is one of the most common cutaneous adverse events, frequently affecting the upper trunk, spreading centripetally, and associated with pruritus.	Macules/papules covering < 10% BSA with or without symptoms (e.g., pruritus, burning, tightness) Erythema covering < 10% BSA with or without symptoms (e.g., pruritus, burning, tightness)	Macules/papules covering 10% - 30% BSA with or without symptoms (e.g., pruritus, burning, tightness); limiting instrumental ADL; Erythema 30% BSA with or without symptoms (e.g., pruritus, burning, tightness); limiting instrumental ADL	Macules/papules covering > 30% BSA with or without associated symptoms; limiting self-care ADL Erythema covering > 30% BSA with or without associated symptoms; limiting self-care ADL	-	-

ADL = active daily living

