6.2.2.6 Adverse Events of Special Interest

AEs of special interest in this study include the following:

1. Anaphylaxis and serious allergic reactions
2. Grades 2 to 5 injection site reaction, including erythema, pain, and induration (see [Appendix 6](#))
3. Drug Induced Liver Injury (DILI) assessed following Hy's Law
4. Malignancy (not including basal cell carcinoma or squamous cell carcinoma of skin)
5. Opportunistic infections such as disseminated histoplasmosis, cryptococcosis, disseminated herpes simplex, disseminated tuberculosis, *Aspergillus* sp., *Candida albicans*, *Coccidioides immitis*, *Cryptococcus neoformans*, *Cytomegalovirus*, *Histoplasma capsulatum*, *Isospora belli*, and *Polyomavirus JC polyomavirus*

6. Cryptosporidiasis

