6.2.2.6.2 Injection Site Reactions

Injection site reactions are to be captured and reported as AEs. These will include Grades 2 to 5 injection site erythema, pain, and induration (see [Appendix 6](#)), which are also captured as Adverse Events of Special Interest (see [Section 6.2.2.6](#)). The Investigator should provide a clear description of the observed or reported AE including location and severity. All concomitant treatments used to treat injection site reactions should be recorded and captured in the eCRF, together with the AE of injection site reactions.

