6.2.7 Injection Site Reactions

Patients will be monitored for local injection site reactions as specified in the Schedule of Assessments (Table 1 and Table 4). Local injection site reactions will be assessed at 2 hours postdose at baseline, and predose for each injection after baseline. Injection site reactions should be managed according to the standard of care. Injection site reactions, Grades 2 to 5, are to be reported as AEs of special interest (see Section 6.2.2.7.3).

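### Appendix 6 grades injection site erythema by percent of whole-body surface and gives induration no criterion, so on their own these two signs cannot in practice reach the Grade 2 that defines the AE of special interest

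*Protocol*

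**What the plan says.** Protocol 6.2.2.6 lists as an AE of special interest "Grades 2 to 5 injection site reaction, including erythema, pain, and induration" and points to Appendix 6. Section 6.2.2.6.2 has injection site reactions captured as AEs and adds "These will include Grades 2 to 5 injection site erythema, pain, and induration", again citing Appendix 6. Section 6.2.7 repeats the rule: "Injection site reactions, Grades 2 to 5, are to be reported as AEs of special interest". Section 6.2.2.7.3 requires special-interest events to be reported immediately or within 24 hours.

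Appendix 6 has three rows.

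- **General injection site reaction.** Erythema appears only as a symptom that may accompany Grade 1 tenderness. Grade 2 is pain, edema, phlebitis or lipodystrophy.
- **Pain.** Grade 2 is moderate pain that limits instrumental activities of daily living (ADL).
- **"Rash maculopapular/Erythema/Induration".** The definition describes a rash "frequently affecting the upper trunk, spreading centripetally, and associated with pruritus". Grade 1 is "Erythema covering < 10% BSA with or without symptoms". Grade 2 is "Erythema 30% BSA with or without symptoms (e.g., pruritus, burning, tightness); limiting instrumental ADL", while macules and papules in the same cell have a range of 10% to 30%. Grade 3 is above 30%. Grades 4 and 5 are blank.

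Section 6.2.2.3 has every AE graded by NCI CTCAE version 4.03 and makes no exception for Appendix 6. On timing, 6.2.7 states: "Local injection site reactions will be assessed at 2 hours postdose at baseline, and predose for each injection after baseline".

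**The concern.** Injection site reactions are a named safety endpoint in both parts (2.1 and 2.2) of a trial that gives up to seven SC injections. Of the three signs that the special-interest definition names, only pain has a usable Grade 2 rule for a local reaction. Erythema is measured against the whole body, on a scale whose definition describes a widespread rash. Induration is named, but no cell says what makes it Grade 1, 2 or 3.

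At stake are the severity grade and the special-interest status of local reactions. A low count of Grade 2 or higher erythema or induration would say more about the scale than about local tolerability. The expedited report to the sponsor would depend on whether the site also happened to be painful or swollen.

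**Working it through.** The protocol gives no figure to reproduce here. The check converts the BSA cut-points into the size of a local patch.

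**Inputs.** The cut-points of 10% and 30% come from Appendix 6. Total BSA is not in the protocol; I assume 1.5 to 2.2 m² for adults.

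**Formulas.** Area = fraction × BSA. Equivalent circle diameter = 2 × √(area / π). Percent of BSA for a patch of diameter d = 100 × π(d/2)² / BSA.

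| Assumed BSA (m²) | 10% BSA (cm²) | Circle (cm) | 30% BSA (cm²) | Circle (cm) | 10 cm patch | 20 cm patch |
|---|---|---|---|---|---|---|
| 1.5 | 1,500 | 43.7 | 4,500 | 75.7 | 0.52% | 2.09% |
| 1.7 | 1,700 | 46.5 | 5,100 | 80.6 | 0.46% | 1.85% |
| 1.9 | 1,900 | 49.2 | 5,700 | 85.2 | 0.41% | 1.65% |
| 2.2 | 2,200 | 52.9 | 6,600 | 91.7 | 0.36% | 1.43% |

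Example: at 1.5 m², 0.10 × 15,000 = 1,500 cm² and 2 × √(1,500/π) = 43.7 cm. A 10 cm patch is π × 5² = 78.5 cm², and 78.5 / 15,000 = 0.52%. Across the whole range a 20 cm patch is at most about one fifth of the Grade 1 limit (2.09 / 10).

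**Reading the table cell by cell.**

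1. Erythema alone: Grade 1 on area in the rash row, and listed only under Grade 1 in the general row.
2. Induration alone: no criterion in any row, so no grade.
3. Erythema or induration with pain or edema: Grade 2 through the general row, or through the pain row if the pain is moderate and limits instrumental ADL.
4. Erythema of 10% to under 30% BSA: no grade as printed.
5. The clause on instrumental ADL follows a semicolon, and the protocol does not say whether it is an added or an alternative condition. If added, Grade 2 is harder still to reach. If alternative, functional limitation could lift erythema to Grade 2 whatever its area, though redness without pain or swelling would seldom limit function (my judgement, not a protocol statement).

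**Timing of dedicated site checks in the POC part (Table 1).** Doses are on Days 0, 30, 60, 90, 120, 150 and 180. Dose 1 has a 2-hour check. There is no site check on Day 15. Doses 2 to 6 are next checked at the following predose visit, about 30 days later. Dose 7 is next checked on Day 210, except in patients who attend the PK visits on Days 187 and 195. Patients outside PK sampling therefore have six of seven doses (2 to 7) with no dedicated check for about 30 days.

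**The case against.** A reader might infer that the special-interest category will stay empty. The protocol does not support that. Section 6.2.2.6 defines a single category for injection site reactions, and the general and pain rows reach Grade 2 without any BSA criterion. A red or indurated site that also hurts or swells qualifies.

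A reader might also infer that these reactions drop out of the safety comparison. They do not. Section 6.2.2.6.2 records all injection site reactions as AEs, the endpoint in 2.1 and 2.2 has no grade floor, and 8.2.5.1 tabulates treatment-emergent AEs by preferred term and by severity. Grade 1 erythema is counted in each arm.

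Nor is induration graded by BSA: its criterion is missing.

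The gap from 10% to under 30% is probably a misprint, given the range for macules and papules in the same cell, and no local reaction would fall in it.

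On timing, 6.2.2.2 collects AEs throughout, with an open question about the time since the last contact, and Day 15 has AE collection and a targeted examination. The MAD schedule (Table 4) also has site checks on Days 7, 187 and 195. An open question, however, does not ask for the extent or grade of a local reaction that has since faded, so it covers the gap only in part.

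All of this narrows the consequence. None of it gives isolated erythema or induration a workable Grade 2.

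**Conclusion.** The point holds in a limited form. Under Appendix 6 as printed, isolated local erythema cannot practically reach Grade 2: the 10% boundary is a circle of about 44 to 53 cm for an assumed BSA of 1.5 to 2.2 m², and no plausible adult BSA changes that. Isolated induration has no grade. The Grade 2 erythema cell is also misprinted or incomplete. For two of its three named signs, the special-interest rule therefore works only through accompanying findings such as pain or edema.

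What is lost is severity grading and the 24-hour special-interest route, not the record of the event. The efficacy analysis is untouched. The size of the effect on the counts cannot be worked out, because the protocol gives no expected rate of injection site reactions. The correction is worth making because the defect sits in a named safety endpoint and is inexpensive to repair.

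**What to change.** 1. **Appendix 6.** Replace the whole-body rash row with contiguous criteria for local erythema and for local induration at the injection site. The sponsor's clinicians should set the thresholds; the protocol offers none to borrow. If any BSA row is kept, correct the Grade 2 erythema cell so that the bands join, and state whether the ADL clause is an added or an alternative condition.
2. **Sections 6.2.2.3, 6.2.2.6, 6.2.2.6.2 and 6.2.7.** Reconcile them with the new table. In particular, say whether Appendix 6 or CTCAE version 4.03 governs the grade of an injection site reaction, and which grades exist for erythema and induration.
3. **Section 6.2.7.** Have each predose check, and the Day 210 check for dose 7, also record the worst reaction since the previous injection and not only what is visible that day.

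**Cost.** One appendix table, matching sentences in four sections, an eCRF field and one question at visits that already take place. More Grade 2 or higher reactions will be reported. The summary of changes for Amendment 5 says that the MAD part has completed, so POC grades will not be directly comparable with MAD grades. Keeping the original Appendix 6 grade alongside the new one in the POC part would preserve that comparison.
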